### 2.2 Hypotheses

**Aim 1: To determine the impact of COIN2DOSE and LOAN2DOSE as compared to control on the trajectory of glycemic control and treatment engagement among adolescents age 12-17 years who are at risk for a near-term rise in A1C.**

Hypothesis 1: Use of COIN2DOSE will result in a lower rise in A1C compared to the controls.

Hypothesis 2: Use of COIN2DOSE will improve engagement as measured by mealtime insulin BOLUS score compared to controls.

Hypothesis 3: Use of COIN2DOSE will yield sustained improvements in A1C trajectory for 12 weeks after the intervention.

Hypothesis 4: Use of COIN2DOSE will yield sustained improvements in BOLUS score for 12 weeks after the intervention.

Hypothesis 5: Use of LOAN2DOSE will result in a lower rise in A1C compared to the controls.

Hypothesis 6: Use of LOAN2DOSE will improve engagement as measured by mealtime insulin BOLUS score compared to controls.

Hypothesis 7: Use of LOAN2DOSE will yield sustained improvements in A1C trajectory for 12 weeks after the intervention.

Hypothesis 8: Use of LOAN2DOSE will yield sustained improvements in BOLUS score for 12 weeks after the intervention.

**Aim 2: To determine the feasibility of COIN2DOSE and LOAN2DOSE interventions in adolescents age 12-17 years who are at risk for a significant near-term rise in A1C.**

Hypothesis 9: The COIN2DOSE intervention will be feasible as determined by 1)  $\geq 75\%$  of participants in the intervention group will complete all study procedures for the duration of the intervention and post-intervention study periods, 2)  $\geq 75\%$  of parents will endorse the feasibility of providing an equivalent economic incentive plan, and 3) no decrease in quality of life at visit 2 compared to baseline (visit 1).

Hypothesis 10: The LOAN2DOSE intervention will be feasible as determined by 1)  $\geq 75\%$  of participants in the intervention group will complete all study procedures for the duration of the intervention and post-intervention study periods, 2)  $\geq 75\%$  of parents will endorse the feasibility of providing an equivalent economic loss aversion plan, and 3) no decrease in quality of life at visit 2 compared to baseline (visit 1).

**Aim 3: To determine user satisfaction with the COIN2DOSE and LOAN2DOSE intervention in adolescents age 12-17 years who are at risk for a significant near-term rise in A1C.**

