Adolescence is a particularly challenging time for individuals with T1D, with average A1C values that are 5% higher than during other periods of childhood and 14% higher than adults (22) (2). Glycemic control worsens from early childhood through age 16-18 (23). It is critically important to develop interventions to prevent deterioration in glycemic control. High glycemic variability is also associated with increased risk of long-term diabetes complications, such as microalbuminuria (24). Lack of adherence to diabetes treatment plans is one of the main causes of sub-optimal glycemic control (3) (25) (7). A significant part of this non-adherence is omission of insulin for ingested carbohydrates at snacks and meals, both by missing boluses entirely and by inaccurate carbohydrate counting (26) (16) (27) (28) (29). Studies have shown significant underestimation of carbohydrate content in meals of up to 20% (26). Furthermore, greater than 33% of adolescents fail to give insulin for >15% of their meals and snacks (16). Adolescents, on average, miss boluses for meals two times per week (28). In one study, youth who omitted insulin at least one time per week had an A1C of 8.8-9.5%, while those who consistently took meal-time insulin had a significantly lower A1C of 7.8-8.0% (28) (30). This is of great significance as poor glycemic control increases risk of both acute and chronic diabetes related complications (31). Meal bolus alarms on insulin pumps, which alarm at a preset time, lead to transient, modest changes in dosing behavior (32). “Lost focus” has been identified as a significant reason for missed meal-time boluses in adolescents (33). Exactly how to effectively maximize engagement with mealtime insulin dosing behavior among adolescents with T1D represents a critical gap in knowledge.

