### 3.2 Rationale

There is an urgent need for a sustainable method that improves patient engagement with delivering mealtime insulin boluses. Improved engagement with mealtime boluses will lead to better glycemic control and will ultimately help reduce the risk of acute and chronic diabetes related complications.

Recent evidence suggests that financial incentives can successfully increase adherence to blood glucose monitoring among adolescents and young adults with type 1 diabetes with moderate to large treatment effect size. Specifically, one study of 10 adolescents evaluated a financial incentive program that delivered \$0.10 per fingerstick blood glucose test, with bonus incentives for  $\geq 4$  tests per day and a maximum achievable incentive of \$251.40 over 12 weeks. The authors found that SMBG increased from  $1.8 \pm 1.0$  to  $4.9 \pm 1.0$  tests per day ( $P < 0.001$ ) with 90% completing four or more tests per day; that mean A1C fell from  $9.3 \pm 0.9\%$  to  $8.4 \pm 1.5\%$  ( $P = 0.05$ ); and that adolescents and parents reported high satisfaction with procedures. In another study, 90 adolescents and young adults demonstrated that a \$60 monthly incentive opportunity significantly increased adherence to glucose monitoring goals in the 90-day incentive period (50.0% vs 18.9%; adjusted difference, 27.2%; 95% CI, 9.5% to 45.0%;  $P = .003$ ). The effect was not sustained during the post-interventional 90-day observation period (15.3% vs 8.7%; adjusted difference, 3.9%; 95% CI, -2.0% to 9.9%;  $P = .20$ ), and A1C did not improve. The evidence to date suggests that it is feasible to increase adherence behaviors among adolescents and young adults with type 1 diabetes. It is unclear whether targeting blood glucose monitoring behaviors is always associated with an improvement in A1C. Whether financial incentives produce a sustained improvement in adherence is also an open question. These methods have not been applied to mealtime insulin dosing behaviors, so whether financial incentives improve adherence to mealtime insulin dosing among adolescents and young adults is also unknown.

There is a strong rationale for targeting adherence to mealtime insulin dosing for improvement. Prior observational research suggests a 1.5% decrease in A1C levels for every one-bolus increase in daily mealtime doses, supporting our premise that increasing mealtime insulin use might help youth who are at risk of increasing A1C(1).

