## 20.0 Data Management and Confidentiality

### 20.1 Statistical Analysis Plan

Database construction and management will involve acquisition of data from each source (see above), imported into Microsoft Excel or an equivalent database program. All analysis will be completed using Stata/SE 15.1 (StataCorp. 2017. Stata Statistical Software: Release 15. College Station, TX: StataCorp LLC), SPSS version 20, SAS version 9.4, other statistical programs as needed. Univariate analysis will be performed on all dependent and independent variables. Analysis includes determining whether the variables have non-normal distributions or outliers. Determinations then will be made as to whether the data transformations are needed. For example, if variance heteroscedasticity, exists, data will be analyzed using log-transformed or other transformations based upon Box-Cox approximations to normal distributions. Measures of other central dependency and dispersion will be evaluated. Primary analyses will be modified intention to treat analysis. All individuals who are randomized will be included in the analysis. A secondary per-protocol analysis may also be performed. Multivariable regression models will be examined to estimate the effects of study variables on the primary outcome – predicted trajectory of glycemic control base on A1C over 90 days – for this sample of T1D patients' data collected at three time points: baseline, 3 months, and 6 months. If the independent variables are highly correlated, we will explore General Linear Models (GLM) or other models. It is possible that Generalized Estimating

Equations (GEE) will be explored for their appropriateness in a larger study and/or for comparisons with the GLM results. Demographic and clinical variables will be entered into models following the independent variable: treatment group assignment. Since time effects may be important in the analyses due to treatments, censoring of data, time sequences, or other reasons, time of observation (i.e. visit 1[day 0], visit 2 [day 90], or visit 3 [day 180]) will also be explicitly accounted for in the regression models. All models will account for the clustering effect of participants having more than one clinic visit during the study timeframe. Additional variables will be collected as listed above. Statistical significance will be  $p<0.5$  (one-sided).

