### *20.2 Power analysis*

To evaluate the primary outcome: glycemic control (measures as predicted trajectory of A1C over 90 days), a multivariable regression model will be developed that accounts for seven independent variables: two primary – adherence and quality of life – and an additional five covariates: participant age, sex, insurance status, intervention/control group status, and time (52). Using an F-test and significant level (alpha) of 0.025, a sample of 20 T1D patients per treatment arm would achieve 74% power to detect an effect size of 0.35 (53). Findings from this pilot study will be used as estimates in planning future studies including recruitment of enough patients to achieve a power of greater than or equal to 80% to evaluate glycemic control (54).

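### The Section 20.2 model for A1C adjusts for adherence and quality of life without limiting them to baseline, so its group term may not estimate the total effect asked by Hypotheses 1 and 5

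*Protocol*

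**What the plan says.** Section 20.2 says that, to evaluate the primary outcome, "a multivariable regression model will be developed that accounts for seven independent variables". These are "two primary – adherence and quality of life – and an additional five covariates", and the five are "participant age, sex, insurance status, intervention/control group status, and time". Randomised group is therefore one covariate among five. No measurement time is given for adherence or quality of life.

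Section 20.1 describes the model differently: "Demographic and clinical variables will be entered into models following the independent variable: treatment group assignment". It names neither adherence nor quality of life. It uses data from baseline, 3 months and 6 months and accounts for time of observation. The list under Covariate Measures in Section 4.0 holds demographics and depression only.

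Elsewhere both terms are outcomes. Hypothesis 2 reads "Use of COIN2DOSE will improve engagement as measured by mealtime insulin BOLUS score compared to controls", and Hypothesis 6 says the same of LOAN2DOSE. Change in BOLUS score at visits 2 and 3 is secondary outcome 6. Hypotheses 9 and 10 require no fall in quality of life at visit 2. Section 3.2 gives the route to lower A1C: better engagement with mealtime boluses, with prior observational work suggesting "a 1.5% decrease in A1C levels for every one-bolus increase in daily mealtime doses".

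**The concern.** Hypotheses 1 and 5 ask whether being assigned to an incentive leads to a smaller rise in A1C than control. That is a total effect, and randomisation protects its estimate. Adherence after randomisation lies on the path from incentive to A1C. Holding it fixed leaves only the part of the effect that does not pass through better dosing, which is a different question. It also gives up the protection of randomisation if adherence and A1C share an unmeasured cause.

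The consequence reaches beyond this pilot. Sections 3.2 and 20.2 say its estimates will be used to power and plan a definitive trial. An attenuated arm effect could misdirect that trial, and a larger sample does not reduce this kind of bias.

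**Working it through.** **1. The plan's own figure.** Section 20.2 gives 74% power from an F-test at alpha 0.025, 20 per arm and effect size 0.35. I used noncentral F power with p = 7 predictors, u tested terms and v = N − p − 1.

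- Three arms (N = 60), 0.35 read as f²: 83.7% for u = 7 and 96.8% for u = 2.
- Three arms, 0.35 read as f: 29.5% for u = 7 and 53.7% for u = 2.
- Two arms (N = 40, v = 32), f² = 0.35, u = 2, noncentrality 0.35 × 32 = 11.2: 73.0%. With noncentrality 0.35 × 40 = 14 it is 83.5%.

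The tested terms, total N and effect metric are not stated, so 74% cannot be settled. The reading closest to the text tests adherence and quality of life rather than group. The rest of this point does not depend on the figure.

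**2. What adjustment for follow-up adherence does.** Let a be the arm effect on daily boluses, b the A1C slope per bolus, and c any effect by other routes. The total effect is T = c + ab and the mediated share is s = ab/T. If adherence is measured with within-arm reliability λ, a linear model holding arm and follow-up adherence gives

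group coefficient = c + ab(1 − λ), so share of T lost = s × λ.

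| Mediated share s | λ = 0.6 | λ = 1 |
|---|---|---|
| 1.00 | 60% | 100% |
| 0.50 | 30% | 50% |
| 0.25 | 15% | 25% |
| 0 | 0% | 0% |

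**3. Illustration from the protocol's figures.** Section 3.1 cites two missed meal boluses a week: 2/7 = 0.286 a day. At 1.5% A1C per bolus (Section 3.2), removing all of them gives 0.286 × 1.5 = 0.43, a total effect of −0.43% A1C. Assumptions: every missed bolus is removed and the observational slope is causal.

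- Full mediation, by formula: 0.00 at λ = 1, −0.43 × 0.2 = −0.09 at λ = 0.8, −0.43 × 0.4 = −0.17 at λ = 0.6.
- Simulation of 4,000 trials, 12 per arm (assumed residual A1C SD 0.8, BOLUS SD 0.6, full mediation): −0.43 unadjusted; 0.00, −0.08 and −0.17 adjusted for follow-up BOLUS at those reliabilities; −0.43 adjusted for baseline BOLUS only.
- Half mediation, by formula: −0.43 × 0.5 = −0.21 at λ = 1 and −0.43 × 0.7 = −0.30 at λ = 0.6.

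**4. A second set of assumptions.** The incentive adds 0.5 bolus a day, bolus SD is 0.8, residual A1C SD is 0.9, and there are two arms of 20, tested one-sided at 0.025. The total effect is 0.5 × −1.5 = −0.75%. Adherence is measured without error.

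| Mediated share | Group coefficient with follow-up adherence | Power without adherence → with |
|---|---|---|
| 100% | 0.01 | 34% → 2.5% |
| 75% | −0.19 | 43% → 9% |
| 50% | −0.38 | 58% → 23% |
| 0% | −0.75 | 73% → 67% |

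Without adherence the coefficient averages about −0.75 in every row.

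**5. Pooling three visits.** If A1C levels from all visits are pooled with group and time as main effects only, the group term averages in a baseline difference of zero. Even with adherence removed, −0.43 becomes −0.43 × 1/3 = −0.14 if the effect is present at visit 2 only, or −0.43 × 2/3 = −0.29 if it is fully sustained at visit 3.

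**The case against.** The strongest reply is that the timing is not stated. Table 1 schedules the quality-of-life questionnaire and a device download at visit 1, so baseline values exist, and adjusting for those would cause no such bias. A separate analysis plan might say so. Section 20.2 is the power section and does not say that its group coefficient decides Hypotheses 1 and 5. Section 20.1 enters group first, which would allow a group estimate before other terms are added. Section 20.2 also does not define adherence as the BOLUS score.

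Most of this stands as a limit on the claim. A reader might infer that the plan does adjust for follow-up adherence, and that a working incentive would be reported as having no effect on A1C. The text supports only that this could happen. What remains is that Section 20.2 presents its model as the way to evaluate the primary outcome, lists time beside two variables that the protocol elsewhere treats as follow-up outcomes, and is not reconciled with Section 20.1. On the definition, Section 3.2 itself speaks of adherence to mealtime insulin dosing as the target.

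A reader might also infer that mealtime dosing is the only path to A1C. Section 3.2 does not say so. The incentive arms are also rewarded or penalised for sharing data, and they upload twice weekly against monthly in control, so some of the effect may arise in other ways.

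**Conclusion.** The point holds as a conditional one. As written, Section 20.2 permits follow-up adherence in the model for A1C. If it enters, the group coefficient is not the effect that Hypotheses 1 and 5 ask about. The attenuation is roughly mediated share times reliability: 30% to 50% at half mediation with reliability 0.6 to 1, near 100% at full mediation with error-free measurement, and nothing if no effect passes through adherence or if only visit 1 values are used. The documents determine neither the share nor the reliability. The contradiction between Sections 20.1 and 20.2 over the role of group needs no assumption.

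Three stronger readings are not supported:

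- A loss of 60% to 100% as a general figure assumes full mediation.
- A group effect of the wrong sign would need an unmeasured common cause whose strength the documents do not give.
- Quality of life as a comparable mediator has no basis: the protocol predicts only no decrease and gives it no path to A1C.

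Nor would deleting adherence be enough by itself if visits are pooled with main effects only, as step 5 shows.

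**What to change.** Align Section 20.2 with Section 20.1:

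- For Hypotheses 1 and 5, make arm the main term, as two contrasts (each intervention against control), on the Section 4.0 primary outcome of A1C change from visit 1 to visit 2. If visits are pooled, use arm-by-time contrasts.
- Adjust only for pre-randomisation variables, including baseline A1C. Allow adherence and quality of life only as visit 1 values, and say so.
- Report follow-up BOLUS score and quality of life against A1C in a separate exploratory mediation analysis that does not decide Hypotheses 1 and 5.
- Restate the power calculation for the arm contrasts, naming the tested terms, total N and effect metric.

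The cost is rewording, a restated power calculation and one extra exploratory model. No further participants, visits or measurements are needed.

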## 4.0 Study Endpoints

### Outcome Measures

Primary outcome:

- 1) Change in A1C ( $\Delta A1C_{90\text{-day}}$ ) from baseline visit (visit 1) to 90-day visit (visit 2).

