### ***Covariate Measures***

Demographics: Age, sex, race, duration of diabetes.

Depression will be measured as a covariate using the validated PHQ-A (which is the Patient Health Questionnaire, PHQ-9, adapted for adolescents) (51). *Note: no notification of medical personnel is necessary if adolescents endorse depressive symptoms because a) the survey does not ask about current suicidal ideation, and b) adolescents in the Children's Mercy Diabetes Center are monitored for depression symptoms at every clinical encounter, with clinical encounters occurring every 3-4 months typically.*

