## **5.0 Study Intervention**

To identify an at-risk population for more intensive intervention opportunities, the Children's Mercy Diabetes Center now routinely uses a validated prediction model based on advanced machine learning (random forest method) and natural language processing to identify individuals who are predicted to experience a rise in A1C in the next 90 days. The model analyzes all patients who presented for a diabetes visit in the prior week. To accomplish this task, the complete health record for the CMH Diabetes Center registry is analyzed. We will select patients from this cohort for recruitment into the present study.

**COIN2DOSE intervention:** From one-week post-randomization to the 12-week study visit, youth randomized to this treatment arm will receive personalized feedback via monetary incentives for dosing insulin at mealtimes. We will define mealtimes based on hour of the day and the presence of a carbohydrate entry associated with the insulin bolus. According to the methodology for calculating BOLUS(1) breakfast will be 0600-1000, lunch will be 1100-1500, and dinner will be 1600-2200. Thus, we will reimburse youth up to \$0.50 per mealtime with at least one meal-associated (carbohydrate-associated) insulin bolus completed (maximum \$1.50/day). We will offer the opportunity for youth to earn a bonus reimbursement of up to \$5.00/week for weeks during which they achieve at least 5 days of 3 mealtime insulin boluses. Finally, we will pay youth up to \$2.00 per week for sharing their insulin use data at least two times per week with the study team during the three-month treatment phase (maximum \$24.00). Therefore, maximum total incentive available is \$210.

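### The A1C change endpoint is to be analysed without visit-1 A1C among the named covariates, which gives up precision that costs almost nothing to recover

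*Protocol*

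**What the plan says.** Section 4.0 defines the primary outcome as the A1C change "from baseline visit (visit 1) to 90-day visit (visit 2"). Most of the secondary outcomes are changes from visit 1 as well.

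Covariates are named in two places:

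- Section 4.0, Covariate Measures: "Demographics: Age, sex, race, duration of diabetes". It continues: "Depression will be measured as a covariate using the validated PHQ-A".
- Section 20.2: a regression that "accounts for seven independent variables: two primary", namely adherence and quality of life, with "an additional five covariates: participant age, sex, insurance status, intervention/control group status, and time".

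Section 20.1 adds a general sentence: "Demographic and clinical variables will be entered into models following the independent variable: treatment group assignment". It also says that the model uses "data collected at three time points: baseline, 3 months, and 6 months", with time of observation and within-participant clustering accounted for. It names no group-by-time term.

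Table 1 in section 10.0 schedules A1C at visits 1, 2 and 3 for all participants. Visit-1 A1C is in neither covariate list. The lists also disagree with each other: race, diabetes duration and PHQ-A are only in section 4.0, and insurance status is only in section 20.2.

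**The concern.** When the endpoint is a change from baseline, the baseline value is the natural covariate. It is measured on the same scale and scheduled for everyone, and a simple change score does not use it optimally. Subtracting baseline amounts to fixing its regression slope at 1. If the true slope is below 1, the subtraction over-corrects and adds noise.

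Arms of 12 to 24 (36 to 72 youths at 1:1:1) leave little precision to spare. The last paragraph of section 3.2 and section 20.2 say that the pilot's estimates will feed the power calculation of a definitive trial, so the way the A1C effect and its variance are estimated matters beyond this study.

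**Working it through.** **The plan's own figure.** The only related figure is the 74% power in section 20.2 (F-test, alpha 0.025, 20 per arm, effect size 0.35). I could not reproduce it on natural readings. With 0.35 as f² and all seven variables tested, power is 56% at N = 40 and 84% at N = 60. With 0.35 as f in a one-way comparison of three arms of 20, it is 54%. The present point does not depend on that figure.

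**Inputs.** From the protocol: 12 per arm (target and minimum) to 24 per arm (maximum), from the Study Summary and section 13.0. Not in the protocol, so assumed: correlation rho of A1C between visits, 0.5 to 0.9; equal variance s² at each visit; s of 1.0 to 1.5 A1C points where a figure in points is given.

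**Step 1: precision.** Apart from the common factor 2/n, the variance of the arm difference is

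- change score: 2s²(1−rho)
- adjusted for visit-1 A1C: s²(1−rho²)
- ratio: (1−rho²) / [2(1−rho)] = (1+rho)/2

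Estimating one pooled slope over three arms multiplies the adjusted variance by about 1 + 1/(N−5) under normality. That is 1 + 1/31 = 1.032 at N = 36 and 1 + 1/67 = 1.015 at N = 72. A simulation agreed with the net ratios to within 0.01.

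| rho | (1+rho)/2 | 12 per arm adjusted is worth, unadjusted (12 ÷ ratio) | net ratio, N = 36 | net ratio, N = 72 |
|---|---|---|---|---|
| 0.5 | 0.75 | 16.0 | 0.77 | 0.76 |
| 0.7 | 0.85 | 14.1 | 0.88 | 0.86 |
| 0.8 | 0.90 | 13.3 | 0.93 | 0.91 |
| 0.9 | 0.95 | 12.6 | 0.98 | 0.96 |

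At N = 36 the gain disappears when (1+rho)/2 × 32/31 = 1, that is at rho of about 0.94.

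**Step 2: the same loss seen as baseline imbalance.** The SD of a chance baseline difference between two arms is s√(2/n): 0.41s at 12 per arm and 0.29s at 24. A change-score contrast keeps −(1−rho) times that difference. For a one-SD imbalance the shift in A1C points is (1−rho) × s√(2/n), shown for s = 1.0 to 1.5:

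| rho | share kept | 12 per arm | 24 per arm |
|---|---|---|---|
| 0.5 | 50% | 0.20–0.31 | 0.14–0.22 |
| 0.7 | 30% | 0.12–0.18 | 0.09–0.13 |
| 0.8 | 20% | 0.08–0.12 | 0.06–0.09 |
| 0.9 | 10% | 0.04–0.06 | 0.03–0.04 |

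This is not a second harm. Since 2(1−rho) = (1−rho²) + (1−rho)², the change-score variance is the adjusted variance plus the variance of this shift. At rho = 0.7, for example, 0.60 = 0.51 + 0.09.

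**Step 3: the model as literally listed.** Suppose group and time enter as main effects over all three visits, with equal correlations and no group-by-time term. The group coefficient is then the arm difference averaged over the visits. Its expected carry-over of a baseline difference is (1 + rho + rho)/3 = (1+2rho)/3, which is 67%, 80%, 87% and 93% at the four values of rho. The sign is not reversed. Simulation gave 0.66, 0.80, 0.87 and 0.93.

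**The case against.** The strongest reply is that the protocol leaves the covariate set open. Baseline A1C is a clinical variable, section 20.1 promises clinical variables without listing them, and a separate analysis plan could name it. That limits the finding but does not remove it. Section 20.2 enumerates seven variables, section 4.0 lists covariates, and the baseline of the primary endpoint is in neither.

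A second reply is that section 20.1 already uses baseline A1C as one of three modelled time points. This would recover the precision if the baseline mean were constrained to be equal across arms, but the protocol states no such constraint. With an unconstrained group-by-time contrast and complete data, the visit-2 comparison is the change-score comparison of Step 1. With no interaction, Step 3 applies.

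A third reply stands: this is a pilot, the gain is modest, and both rho and the A1C SD are assumed. The largest shift in Step 2 (0.31 points) pairs the lowest rho with the highest SD at minimum enrolment.

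A reader might infer more than the documents support:

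- *That chance imbalance passes straight into the A1C effect, or biases it.* For a change score only (1−rho) of it remains, with reversed sign, and randomisation keeps the comparison unbiased. Near one-for-one carry-over needs the literal main-effects model.
- *That the machine-learning forecast should also be a covariate.* Section 5.0 says the model serves "to identify individuals who are predicted to experience a rise in A1C in the next 90 days". It does not say that a numeric forecast is kept for each participant, and Table 1 has no such item. Entry criterion 5 (section 11.0) accepts a current A1C above 7.2% and/or a predicted rise, so the forecast need not have selected every youth.
- *That insurance status should be dropped as a weak predictor.* Nothing in the protocol shows this.
- *That every secondary change outcome should be adjusted for its first value.* Table 1 randomises at visit 1 and places the first CGM a week after enrolment, while section 5.0 starts the intervention a week after randomisation. On that reading the first CGM wear may overlap treatment. Section 6.0 gives a different order, so adjustment is safe only where the baseline clearly comes first.

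**Conclusion.** The point holds as an improvement in efficiency and specification. The protocol names the covariates for an A1C change endpoint twice and omits visit-1 A1C both times. Adjustment would cut the variance of the arm contrast by 5% to 25% for assumed rho of 0.9 to 0.5, before the cost of one slope. After that cost the cut is about 2% to 23% at 36 participants and 4% to 24% at 72. These figures rest on equal visit variances and an assumed rho, and the gain is small if rho is near 0.9. No bias is claimed. If the listed terms are the whole model, without a group-by-time term, the group coefficient is considerably more exposed to chance baseline differences (67% to 93% carried over). The protocol should rule that reading out.

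**What to change.** 1. In sections 20.1 and 20.2, name visit-1 A1C as a mandatory covariate of the primary A1C model. Use visit-2 A1C (and visit-3 A1C for the later comparison) as the outcome, and do not also keep visit-1 A1C as an outcome row. If visits 2 and 3 are modelled together, include a group-by-visit term so that the visit-2 effect can be read off.
2. Do the same for those secondary change outcomes whose baseline is measured before randomisation or before the intervention starts. For the CGM outcomes, first reconcile the order of sensor wear, randomisation and intervention start across sections 5.0, 6.0 and 10.0.
3. Bring the Covariate Measures list and the section 20.2 list into one.
4. Add the forecast A1C change only if a numeric value from before randomisation is held for every participant.

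The cost is wording and one degree of freedom in the primary model. Visit-1 A1C is already scheduled for all participants.

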The objective of the present study is to obtain pilot feasibility data to 1) determine whether COIN2DOSE and/or LOAN2DOSE show a preliminary trend for improvement in the outcomes of interest, 2) perform power calculations that will inform the design of a definitive trial(s) and 3) establish feasibility of the interventions and study procedures to inform the design of a definitive trial(s).

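### The 74% power in Section 20.2 is not power for either intervention arm against control on 90-day A1C change, and it is quoted only for 20 per arm when the target is 12 per arm

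*Protocol*

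**What the plan says.** Section 20.2 opens with "To evaluate the primary outcome: glycemic control (measures as predicted trajectory of A1C over 90 days") and describes a regression with seven independent variables. Two of them, adherence and quality of life, are called primary. The rest are an "additional five covariates: participant age, sex, insurance status, intervention/control group status, and time". For an F-test at alpha 0.025 it reports that "a sample of 20 T1D patients per treatment arm would achieve 74% power to detect an effect size of 0.35". It does not say whether 0.35 is Cohen's d, f or f², which terms are tested, or what the total N is. It goes on to say that the pilot findings will serve as estimates for planning future studies, including "recruitment of enough patients to achieve a power of greater than or equal to 80% to evaluate glycemic control".

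Elsewhere the protocol sets a different target of inference. Section 4.0 defines the primary outcome as change in A1C "from baseline visit (visit 1) to 90-day visit (visit 2"). Hypothesis 1 in Section 2.2 is "Use of COIN2DOSE will result in a lower rise in A1C compared to the controls" and Hypothesis 5 is "Use of LOAN2DOSE will result in a lower rise in A1C compared to the controls". Section 20.1 makes treatment group assignment the independent variable, with demographic and clinical variables entered after it.

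On size, Section 13.0 gives a target of 36 and a maximum of 72, and Section 11.0 gives 1:1:1 allocation to three arms. Section 15.0 refers to 40 participants and to stipend funds for 4 additional subjects.

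**The concern.** The only power figure in the protocol sits under the primary outcome but belongs to a model in which treatment is an adjustment variable. One intervention/control indicator also cannot carry two separate contrasts in a three-arm trial. A reader will naturally take 74% as the chance of detecting an intervention effect on A1C.

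That reading has a cost because the pilot is meant to "perform power calculations that will inform the design of a definitive trial(s"). Set beside an aim of at least 80%, a figure of 74% suggests that the pilot is almost large enough: at a fixed effect, going from 74% to 80% power takes only about 14–16% more patients. The arm-versus-control comparisons may be much further from 80% than that.

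The stated 20 per arm, 60 in total, is inside the permitted range, but it is neither the target and minimum (36) nor the maximum (72).

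**Working it through.** **Inputs.** From Section 20.2: F-test, alpha 0.025, effect 0.35, 20 per arm, seven predictors, 74%. From Sections 11.0 and 13.0: 36/3 = 12 and 72/3 = 24 per arm. The protocol gives no SD for A1C change, so differences are in SD units.

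**1. Can the 74% be reproduced?** Take adherence and quality of life as the two tested predictors out of seven, with f² = 0.35, alpha 0.025, numerator df u = 2 and denominator df v = N − 8. The noncentrality is λ = f²·v, f²·(u+v+1) or f²·N, depending on convention.

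| Total N | Power over the three conventions |
|---|---|
| 36 | 65.3%, 70.6%, 78.0% |
| 40 | 73.0%, 77.5%, 83.5% |
| 60 (three arms of 20) | 93.9%, 95.2%, 96.8% |

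A 7-df test of the whole model at N = 60 gives 76.3% to 83.7%. The nearest match is therefore N = 40, two arms of 20, under one convention. That is a possible origin and no more, because the metric, tested terms and N are unstated. For the same reason the 74% cannot be shown to be miscalculated.

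**2. Can it be read as arm-versus-control power?** Use an unadjusted two-group comparison with n per arm: F with 1 and 2n − 2 df, λ = (n/2)·d², alpha 0.025. The three readings of 0.35 are f² (d = 2√0.35 = 1.183), f (d = 2 × 0.35 = 0.70) and d itself (0.35). At n = 20, λ is 10 × 1.183² = 14.0, 10 × 0.70² = 4.9 and 10 × 0.35² = 1.225.

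| n per arm | 0.35 is f² | 0.35 is f | 0.35 is d |
|---|---|---|---|
| 12 | 68.8% | 26.6% | 7.7% |
| 20 | 91.5% | 46.0% | 12.1% |
| 24 | 95.9% | 54.7% | 14.4% |

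With a one-sided t-test at 0.025, the n = 20 row becomes 95.4%, 57.8% and 18.9%. A three-arm omnibus test (2 df, N = 60, alpha 0.025) gives 96.9% if f² = 0.35 and 54.0% if f = 0.35. None of these treatment readings gives 74% at 20 per arm.

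**3. What can the trial estimate?** The 95% CI half-width for a difference between two arms is t(0.975, 2n − 2)·√(2/n) SD. At n = 12 this is 2.074 × 0.408 = 0.847, and at n = 24 it is 2.013 × 0.289 = 0.581. The 9 and 18 per arm rows assume that 25% of 90-day A1C values are missing (12 × 0.75 and 24 × 0.75). The detectable difference is from the noncentral t distribution with 74% power.

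| n analysed per arm | CI half-width (SD) | Detectable, one-sided 0.025 (SD) | Detectable, F-test 0.025 (SD) |
|---|---|---|---|
| 9 | 1.00 | 1.31 | 1.48 |
| 12 | 0.85 | 1.11 | 1.25 |
| 18 | 0.68 | 0.89 | 1.00 |
| 20 | 0.64 | 0.845 | 0.94 |
| 24 | 0.58 | 0.77 | 0.86 |

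**4. How far from 80%?** At a fixed effect, N scales as (z₁₋α + z_power)². At one-sided 0.025, moving from 74% to 80% multiplies N by 1.16. For the F-test at 0.025 (two-sided) the factor is 1.14. Compare this with power for assumed true differences (one-sided 0.025):

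| Assumed difference | Power at 12 per arm | Power at 24 per arm | n per arm for 80% |
|---|---|---|---|
| 0.35 SD | 13% | 22% | 130 |
| 0.50 SD | 22% | 40% | 64 |
| 0.70 SD | 37% | 66% | 34 |

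**The case against.** The strongest reply is that this is a pilot. It seeks a preliminary trend, feasibility data and inputs for later power calculations, and Section 2.1 leaves efficacy to a fully powered trial. No go/no-go rule or sample-size decision rests on the 74%, and low power for a contrast is no defect in such a study. That stands, and no more patients are asked for. It does not excuse a power figure that is placed under the primary outcome but describes something else.

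Second, no arithmetic error is proved: a 2-df test at N = 40 or a whole-model test at N = 60 comes close to 74%. This also stands. The fault is a mismatch between the figure and the comparison, and neither of those tests is a test of treatment.

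Third, 20 per arm lies within 36–72, and Section 20.2 says only what 20 per arm would achieve. True, but the reader still has no figure for the stated target.

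Fourth, the scale-up argument assumes that someone will extrapolate from 74%, whereas Section 20.2 says the pilot's findings will supply the estimates. The risk is one of misreading, and the assumed differences have no source in the protocol, which is why a range is shown.

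Finally, the two-group t comparison is simpler than the regression planned in Section 20.1. It is a transparent reference calculation. Covariate adjustment could narrow the intervals, but the protocol gives no correlation from which to say by how much.

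**Conclusion.** The point holds. Section 20.2 is wrong as written: its 74% is not power for COIN2DOSE or LOAN2DOSE against control on 90-day A1C change, and it is given at a size that is neither the target nor the maximum. No pairwise or omnibus treatment reading at 20 per arm yields 74%; the F-test readings at alpha 0.025 run from 12% to 97%. At the target of 12 per arm, each contrast has a 95% CI half-width of about 0.85 SD and needs a difference of about 1.11 SD for 74% power at one-sided 0.025.

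These figures rest on an unadjusted two-group comparison with equal arms and complete 90-day A1C data, except where 25% missing is assumed. The conclusion about which comparison is powered rests on the text alone and needs none of these assumptions. The statement should be corrected, but it does not threaten the conduct of the trial.

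**What to change.** Replace the 20-per-arm, 74% and seven-predictor text in Section 20.2 with a statement for each arm-versus-control difference in 90-day A1C change. Name the model, alpha and sidedness, and count participants with a 90-day A1C. Suggested wording:

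> With 12 to 24 participants per arm providing a 90-day A1C, an unadjusted two-group t comparison of each intervention arm with control has a 95% CI half-width of about 0.85 to 0.58 SD (1.00 to 0.68 SD if 25% of 90-day values are missing).

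If a power statement is kept, add:

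> At one-sided 0.025, 74% power needs a difference of about 1.11 SD at 12 and 0.77 SD at 24 per arm.

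If the non-directional F-test at 0.025 is retained instead, the corresponding values are 1.25 and 0.86 SD. The alpha should be the same as the corrected threshold in Section 20.1, whose p<0.5 is a separate error. Section 15.0 should say how its 40 participants relate to the 36–72 range, for example whether they are the 36 plus the 4 additional subjects.

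The cost is protocol wording only. The arms, endpoint, 36–72 range and analysis stay as they are.
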